Post Authorization Safety Study (PASS) Information

Acronym/Title	Risk association of orofacial cleft and G lu c oc o rti c oids exposure during pregnancy: a meta-analysis			
Protocol version and date	1.2, 16 November 2018			
IMPACT study number	20638			
Study type / Study phase	Observational, Meta-analysis of published literature			
EU PAS register number	TBD, Study not yet registered			
Active substance	Diflucortolone valerate (BAY 866146); Glucocorticoids (drug class: corticosteroids)			
Medicinal product	Nerisona			
Product reference	BAY 866146			
Procedure number	NA			
Comparator / Reference therapy	Unexposed control			
Study Initiator and Funder	Bayer AG			
Research question and objectives	A systematic literature review was conducted to identify evidence on the risk of development of cleft palate in neonates after glucocorticoids exposure during pregnancy. The published meta-analyses are outdated and have some shortcomings. Evidence gathered from systematic literature review is heterogeneous and does not answer the question. Thus, a meta-analysis of the evidence identified in the systematic literature review is warranted. The primary objective of this meta-analysis is to investigate the relationship between the exposure of glucocorticoids during pregnancy and orofacial cleft development. Secondary objectives are to perform subgroup analyses for: • Potency of glucocorticoid • Route of administration • Types of orofacial cleft			
Country(-ies) of study	NA			

Author

Marketing authorization holder

Marketing authorization holder(s)	Bayer AG
MAH contact person	

The study will be conducted in compliance with the protocol and any applicable regulatory requirements.

Throughout this document, symbols indicating proprietary names (®, TM) may not be displayed. Hence, the appearance of product names without these symbols does not imply that these names are not protected.

1. Table of contents

1.	Table of contents3	
2.	List of abbreviations	4
3.	Responsible parties	5
3.1	Study initiator and funder	5
4.	Abstract	6
5.	Amendments	9
6	Milestones	0
U.		
7.	Rationale and background	9
8.	Research questions and objectives	.11
8.1 0 2	Primary objective	.11
0.2	Secondary objective	.11
9 .	Research methods	.11
9.1	Study design	.11
9.2	Selection criteria used for the Systematic Literature Review (SLR)	12
9.2.	2 Representativeness	.12
9.3	Variables	.13
9.3.	1 Exposure definition	.13
9.3.	2 Outcomes definition	.13

3.1 Study initiator and funder

Role:	OS Conduct Responsible
Name: E-mail:	
Role:	Qualified Person responsible for Pharmacovigilance (QPPV)
Name:	
Role:	MAH contact person (Regulatory Affairs)
Name:	
Role:	OS Safety Lead
Name:	
Role:	OS Medical Expert
Name:	
Role:	OS Statistician
Name:	
Role:	OS Epidemiologist
Name:	
Role:	OS Health Economics and Outcomes Research (HEOR) responsible
Name:	

4. Abstract

Acronym/Title	Risk association of orofacial cleft and glucocorticoids exposure during pregnancy: a meta-analysis				
Protocol version and date	1.2, 16 November 2018				
IMPACT study number	20638, EU PAS TBD				
Study type / Study phase	Observational, Meta-analysis of published literature				
Author					
Rationale and background	Glucocorticoids use is very common in early pregnancy or first trimester. The studies identified in a systematic literature review present an unclear picture of potential effects of glucocorticoids use during pregnancy on the orofacial developmental process in infants. Bayer's glucocorticoid product, Nerisona (INN) Diflucortolone valerate (for topical use) is contraindicated for use during pregnancy. In the scope of a regulatory procedure, the French Health Authority has requested Bayer to conduct a meta- analysis encompassing all studies investigating a possible increase in the risk of cleft palates in neonates of women treated with glucocorticoids during the first trimester of pregnancy. A meta-analysis with most recent published data will support drawing evidence-based conclusions and answer questions about the impact of glucocorticosteroid use during pregnancy				
Research question and objectives	The analysis' primary objective is to conduct a meta-analysis to investigate the relationship between the exposure of glucocorticoids during early pregnancy or first trimester and congenital orofacial cleft development. Secondary objectives are to perform subgroup analyses for: • Potency of glucocorticoid • Route of administration • Types of orofacial cleft				
Study design	A meta-analysis of published literature will be conducted with 18 shortlisted observational studies identified through a Systematic Literature Review (SLR) which was conducted using keyword and MeSH terms on Embase and Medline via Ovid®. Articles published up to 25 June 2018 have been reviewed.				

Population	Pregnant women exposed to any glucocorticoid or corticosteroid or steroids in early pregnancy or first trimester of pregnancy irrespective of mode of administration identified from articles published up to 25 June 2018 by pre-specified inclusion and exclusion criteria				
Variables	 Exposure definition First trimester exposure Early pregnancy Outcomes definition Oral clefts Cleft lip with or without palate Cleft palate Covariate definition Potency of glucocorticosteroids Route of administration of glucocorticosteroids 				
Data sources	 Embase and Medline via Ovid®, Cochrane database, Google Scholar has been used for data collection All records retrieved from the literature searches have been screened for relevancy based on eligibility criteria (inclusion/exclusion). Relevant back references from the shortlisted studies have also been reviewed. 				
Study size	18 observational studies have been selected for meta-analysis by predefined eligibility criteria in a previously conducted SLR.				
Data analysis	 Direct treatment comparison: Any glucocorticoid or corticosteroid or steroids use irrespective of mode of administration vs. no use of glucocorticosteroids Model: Fixed effect model Measure of relative effect: For the dichotomous outcomes will be assessed by Odds ratio (OR) Inverse variance method Effect size are assessed by Odds ratio (OR) as it is a rare outcome Publication bias: Using funnel plot, Egger's test, Galbraith plot Sensitivity analysis Sub-group analyses Route of administration: Types of orofacial cleft Potency of glucocorticoid 				

	 Data will be analysed by using the metafor package in R software version 3.5.1 The results of the outcomes will be described as eman with 95% credibility intervals (CI) and presented as Forrest plots 			
Milestones	Start of data collection (SLR): 12 June 2018			
	End of data collection (SLR): 25 June 2018			
	Final report (SLR): 9 July 2018			
	Meta-analysis protocol: 09 November 2018			
	Statistical analysis plan: 10 September 2018			
	Meta-analysis report: November 2018			

5. Amendments

Not applicable.

6. Milestones

Table 1 presents the planned milestones for the project. These milestones are based on a timely review and approval of the project. Administrative changes to milestones due to delays in study preparation, data release and analysis do not require amendments to the protocol.

Table 1: Milestones

Milestone	Planned date
Start of data collection (SLR)	12 June 2018
End of data collection (SLR)	25 June 2018
Final report of study results (SLR)	9 July 2018
Meta-analysis protocol	16 November 2018 (version 1.2)
Registration in the EU PAS register	TBC
Statistical analysis plan	10 September 2018
Meta-analysis report	November 2018

7. Rationale and background

Cleft lip and palate are the most common congenital anomalies of the craniofacial regions occurring at a rate of 1 in 700 births (1-3). Unilateral cleft lip and palate is the most common diagnosis followed by isolated cleft lip. It is more common in males. (4). The most common manifestation of these anomalies is difficulty in feeding. Individuals also experience speech, hearing and dental problems (5).

The development of cleft lip and palate is well documented. Between 4-8 weeks of gestation, normal lip development occurs along with frontonasal prominence. Nasal placodes develop and divide the paired medial and lateral nasal processes (5, 6). By the end of week 6 of gestation, the primary palate is formed by the fusion of paired medial processes and developing premaxilla (central upper lip, maxillary alveolar arch and four incisor teeth, and hard palate). During week 6-12, the secondary palate develops along with medial projections of maxillary processes. Cleft of lip and/or palate is a result of the disruption of normal development which could be due to chemical and environmental factors(7, 8)

Corticosteroids have a wide range of clinical uses. However, its use in pregnancy is limited (9).

Corticosteroids fluctuate in their ability to cross the placenta (10). Fetal concentrations (although lower than maternal concentrations) are linearly related to maternal (cortisol) concentrations (11). Pregnancy enhances systemic absorption of inhaled corticosteroids as it increases maternal tissue perfusion. This leads to the assumption that exposure of corticosteroid in pregnancy might cause congenital anomalies (11-13).

Some epidemiological studies have reported 3-6 fold increased risk of orofacial cleft due to corticosteroid use in early pregnancy or in first trimester in humans (14-16), while, some studies have not found this association (16, 17). Thus, there remains a controversy on the implication of glucocorticoid use in pregnancy. Therefore, it is important to gather more evidence related to the risk of cleft palate in neonates following exposure to glucocorticoids during pregnancy.

Bayer's glucocorticoid product, Nerisona (INN) Diflucortolone valerate (for topical use) is contraindicated for use during pregnancy. In the scope of a regulatory procedure, the French Health Authority has requested Bayer to conduct a meta-analysis encompassing all studies investigating a possible increase in the risk of cleft palates in neonates of women treated with glucocorticoids during the first trimester of pregnancy.

In response to this request, a systematic literature review (SLR) was conducted to identify relevant studies evaluating the potential association between the exposure to glucocorticoids and the occurrence of orofacial cleft. Due to the heterogeneity findings in the 18 selected publications, a meta-analysis of their results was deemed as warranted and will be conducted as originally requested. Since this analysis will evaluate the risks of a medicinal product class used in a patient population for which safety information is limited or missing (e.g. pregnant women), it is considered as a Post Authorization Safety Study (PASS), in accordance with the European Medicine Agency Guideline on good pharmacovigilance practices (GVP) Module VIII – Post -authorisation safety studies (Rev 3) (18).

Of note, a meta-analysis for topical administration of corticosteroids during early pregnancy is not published. Nevertheless, a meta-analysis (16) was identified in the SLR that discusses effect of use of corticosteroids during early pregnancy without specifying the route of administration. This meta-analysis also has some shortcomings such as:

- Relationship between dosage and duration of medication were not examined in the included studies that could affect their results
- Confounding factors, such as race, maternal age, level of education, economic and social status, smoking, chances of repetitive enrollment of some patients in different studies were not addressed
- Dosage of glucocorticoid was not discussed
- Recall and publication bias due to retrospective design

Thus, further analyses are warranted to investigate a concrete association between the exposure to glucocorticoids and the developmental orofacial cleft. The current meta-analysis aims to also address some of the shortcoming of the existing meta-analysis such as the confounder effect by subgroup analyses. However, not all shortcomings will be addressed due to lack of data availability in the published literature.

8. Research questions and objectives

The studies identified and reported in a previously conducted SLR do not represent a clear scenario regarding the risk association of glucocorticoids exposure during pregnancy (see Appendix 1). The individual studies reported high to non-significant risk of cleft development in pregnant women exposed to glucocorticoids in comparison to non-exposed pregnant women. Consequently, it is difficult to draw a clear conclusion from these studies without pooled analysis of their findings.

8.1 **Primary objective**

The primary objective in this study is:

• To conduct a meta-analysis of published literature to investigate the association between the exposure of glucocorticoids during pregnancy and orofacial cleft development

8.2 Secondary objective

The secondary objective of this study is:

• To perform sub group analyses for mild, moderate and strong glucocorticoid types as well as for route of administration and types of orofacial cleft.

9. **Research methods**

9.1 Study design

Meta-analysis will be conducted with 18 observational studies previously identified through a systematic literature review which was conducted using keyword and MeSH terms on Embase and Medline via Ovid® (see Appendix 1).Articles published up to 25 June 2018 have been reviewed. Additionally, a supplementary search was conducted on the Cochrane database and general sources such as Google Scholar to identify additional studies that might be relevant to the scope of the search.

All records retrieved from the literature searches were screened for relevancy based on eligibility criteria (inclusion/exclusion). The results were initially screened by title and abstract, and the shortlisted results were further screened on full text. Relevant back references from the shortlisted studies have also been reviewed. The key outcomes reported were OR followed by RR for developing orofacial cleft(s) in neonates due to exposure of women to glucocorticoids in pregnant women

Meta-analysis is a powerful tool to analyse rare outcomes as individual studies provide inadequate power to test rare outcome. Meta-analysis increase precision in estimating effects.

9.2 Setting

Pregnant women exposed to any glucocorticoid or corticosteroid or steroids in early pregnancy or first trimester of pregnancy irrespective of mode of administration identified through a systematic review of articles published up to 25 June 2018 by pre-specified inclusion and exclusion criteria (see section 4 of SLR in see Appendix 1). In total 18 observational studies have been selected for this meta-analysis with sample size for individual studies ranging from 106 to 832,636 patients.

- Source: Embase and Medline via Ovid®, Cochrane database, Google Scholar
- *Population sampling strategy:* All records retrieved from the literature searches were screened for relevancy based on eligibility criteria (inclusion/exclusion). The results were initially screened by title and abstract, and the shortlisted results were further screened on full text. Relevant back references from the shortlisted studies have also been reviewed.

9.2.1 Selection criteria used for the Systematic Literature Review (SLR)

The inclusion and exclusion criteria used for the selection of studies as well as detailed methodology of the systematic literature review are provided in the Appendix 1.

No time period restriction was used. The systematic literature review was conducted to identify all studies (including observational studies and clinical trials) published till 25 June 2018 (search date). In addition, there were no restrictions to the route of administration.

Only 18 studies were shortlisted based on the inclusion criteria. All of the 18 studies were observational studies while no clinical trials were identified that met the inclusion criteria.

The selection criteria utilized in the SLR were the following:

Inclusion criteria

- Population: Pregnant women
- Intervention: Any glucocorticoid or corticosteroid or steroids use irrespective of mode of administration
- Comparator: Any/none
- Outcomes: Incidence/ risk of cleft lip/palate in infants
- Study Design:
 - Meta-analysis and systematic literature reviews
 - Observational studies (such as cohort study, case-control study, registries data)
 - Clinical trials Phase IIb, III, and IV
 - Conference abstracts/posters
- Time period: No time period restriction
- Geography: No geography restriction

Exclusion criteria

- Population: Nonpregnant women
- Intervention: Drugs other than glucocorticoid or corticosteroid or steroid
- Outcomes: Incidence/ risk of cleft lip/palate in infants
- Study Design:
 - Animal Study

- In vitro studies
- o Editorial, letters, comment
- Clinical trials Phase I or preclinical
- Case reports, case series
- o Reviews
- Studies focusing on:
 - Diagnosis and surgical procedure for cleft repair
 - o Impact of Increased internal corticosteroids due to stress
 - The relationship between genetic mutations and cleft patients
 - Adverse events for other drugs
 - Safety profiles of glucocorticoid or corticosteroid

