9.3 Variables

9.3.1 Exposure definition

The primary exposure of interest is glucocorticoid use.

• First trimester exposure: At least one prescription for glucocorticosteroids redeemed from the first day of the last menstrual period to the end of gestational week 12

OR

• Early pregnancy: At least one prescription for glucocorticosteroids redeemed from 30 days before estimated conception to the end of the first trimester

Our primary comparison group includes women not using glucocorticoid during pregnancy.

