9.3.2 Outcomes definition

The primary outcome variable is the incidence of any type of orofacial cleft. Oral clefts are defined as diagnosis of cleft lip with or without cleft palate or isolated cleft palate.

Please refer to section 4 of systematic literature review report provided in Appendix 1 for the detailed scope of the research.

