9.7 Data analysis

- Direct treatment comparison: Any glucocorticoid or corticosteroid or steroids use irrespective of mode of administration vs. no use of glucocorticosteroids
- Model: Fixed effect model will be used. We assume that the underlying effect size is the same across the studies. The differences in observed effects are only due to random error or sampling error within the studies. The observed effects mainly depend on the sample size and weighted average mean might give a precise estimation of the overall effect. However, any deviation from this assumption will be discussed.
- Measure of relative effect: For the dichotomous outcomes will be assessed by Odds ratio (OR). Given that the event of our interest is a rare outcome, we assume relative risk (RR) equivalent to OR.
- Inverse variance method: Studies with less variance or standard deviation are given more weight. The variance of weighted average can be minimized through this method and hence inverse variance method will be used to assess the direct treatment effect
- Effect size is assessed by Odds ratio (OR) as it is a rare outcome
- Publication bias: Reporting or publication bias will be assessed by using the funnel plot (symmetry or asymmetry) and it again confirmed by using the Egger's test (in case of asymmetry funnel plot). Further, any outliers in the effect size will be determined by Galbraith plot
- Sensitivity analysis: In order to know the robustness of the findings, sensitivity analysis will be performed with and without outlier studies so that any uncertainty can be determined. This will be done only in case of high level of heterogeneity observed. However, plausible reasons for high heterogeneity (unexplained variation) will be discussed in the MAR
- Sub-group analyses will be performed for
 - Route of administration:
 - Topical
 - Systemic
 - Any other form of use
 - Types of orofacial cleft
 - Cleft lip (CP)
 - Cleft lip with or without palate (CLP)
 - Cleft palate (CP)
 - Orofacial cleft (OC)
 - Potency of glucocorticoid
 - Mild
 - Moderate
 - Potent
 - Very potent
- 95% credibility intervals will be used as a measure for the expression of the difference (overlap / no overlap with 1 for OR)
- Data will be analysed by using the metafor package in R software version 3.5.1

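### Sections 9.2.1 and 9.7 do not prevent studies with malformed-infant controls from being pooled, as one common effect, with studies that use all or non-malformed births

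*Protocol*

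**What the plan says.** Protocol section 9.2.1 lists the selection criteria of the literature review. Among eligible designs it names "Observational studies (such as cohort study, case-control study, registries data"; the comparator criterion is "Comparator: Any/none". No inclusion or exclusion item concerns the infants who do not have a cleft. The result was 18 studies: "All of the 18 studies were observational studies while no clinical trials were identified that met the inclusion criteria".

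Section 9.3.1 defines the comparison group by the mother's exposure: "Our primary comparison group includes women not using glucocorticoid during pregnancy". Section 9.3.2 defines the outcome: "The primary outcome variable is the incidence of any type of orofacial cleft", and "Oral clefts are defined as diagnosis of cleft lip with or without cleft palate or isolated cleft palate". Neither section defines a non-case.

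Section 9.7 uses an inverse-variance fixed-effect model and says: "We assume that the underlying effect size is the same across the studies". Its subgroups are route, cleft type and potency. Its only sensitivity analysis removes outliers, and only if heterogeneity is high.

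Section 7 (Rationale and background) says, after a passage on absorption and placental transfer: "This leads to the assumption that exposure of corticosteroid in pregnancy might cause congenital anomalies".

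**The concern.** In a case-control study the control series decides what the odds ratio estimates. Controls drawn from all births, or from births without malformations, give the odds ratio for cleft (for a rare outcome, near enough the same quantity). Controls drawn from infants with other malformations give the odds ratio for cleft relative to those malformations. The two agree only if exposure is unrelated to the control malformations.

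Section 7 leaves open that exposure might cause congenital anomalies. If that reaches beyond clefts, malformed controls are exposed more often than the source population and the cleft odds ratio comes out too low. This is a safety study requested by a health authority, and an error in that direction can hide harm.

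Recall bias, which section 9.9 names for retrospective case-control studies, works the other way. Mothers of healthy controls may recall medication less completely than mothers of cases, which raises the odds ratio. Mothers of malformed controls can be expected to recall more as case mothers do. A single pooled figure shows neither effect.

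**Working it through.** The protocol gives no figure on this point, so there is nothing to reproduce. The size below is an illustration on assumed values.

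**Inputs**
- From the protocol: 18 observational studies (9.2.1); inverse-variance fixed-effect pooling on the OR scale (9.7).
- Assumed: true OR(cleft) = 1.5; OR(other), the effect of exposure on the control malformations, = 1.0, 1.2 or 1.5; *w*, the share of total weight held by malformed-control studies, = 0, 25%, 50% or 75%. The protocol gives none of these.

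**Step 1: one malformed-control study.** The observed OR is the exposure odds in cleft cases over the exposure odds in malformed controls. Dividing both by the exposure odds in non-malformed births gives

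OR(observed) = OR(cleft) / OR(other).

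With OR(cleft) = 1.5 this is 1.5/1.2 = 1.25 or 1.5/1.5 = 1.00.

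**Step 2: the pooled value.** A fixed-effect model averages log odds ratios by weight:

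OR(pooled) = exp[(1 − w) ln OR(cleft) + w ln(OR(cleft)/OR(other))] = OR(cleft) × OR(other)^(−w).

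| OR(other) | w = 0 | w = 25% | w = 50% | w = 75% |
|---|---|---|---|---|
| 1.0 | 1.50 | 1.50 | 1.50 | 1.50 |
| 1.2 | 1.50 | 1.43 | 1.37 | 1.31 |
| 1.5 | 1.50 | 1.36 | 1.22 | 1.11 |

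For example, 1.5 × 1.2^(−0.25) = 1.433 and 1.5 × 1.5^(−0.50) = 1.225. The first row and first column are the no-bias cases.

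**Step 3: would the planned analyses show it?**
- The subgroups in 9.7 do not sort studies by control type.
- The outlier analysis sorts studies by result, and runs only under high heterogeneity.
- Section 9.8 plans a Newcastle-Ottawa appraisal but attaches no consequence for inclusion, weighting or stratification.
- Section 9.9 names recall and publication bias for case-control studies, not the choice of controls.
- Item 7.2 of the ENCePP checklist (Annex 2) answers No on whether selection bias is addressed.

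**Step 4: cost of a split.** The pooled SE is 1/√(total weight). A stratum holding share 1 − w has its SE multiplied by 1/√(1 − w): 1/√0.75 = 1.15, 1/√0.50 = 1.41 and 1/√0.25 = 2.0 for the non-malformed stratum when w is 25%, 50% or 75%.

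**The case against.** The strongest objection is that the key fact is absent. A reader might infer that studies with malformed controls are among the 18 and are in fact pooled. The protocol does not say so, and the literature review report (Appendix 1) is not shown. This objection stands: the point concerns what the plan permits.

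A reader might also infer that registry data must mean malformed controls. They need not. Section 9.2.1 does not say what kind of registry is meant, and cases from a malformation registry can be compared with births sampled outside it. The definition of exposure by redeemed prescriptions (9.3.1) and a study of 832,636 patients (9.2) do not point to malformation-only registries, though they do not settle the control type.

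A third tempting reading is that section 7 asserts a general teratogenic effect, so that the plan contradicts itself. It says only that exposure might cause congenital anomalies, in a section that is mainly about clefts, and can be read as meaning clefts. There is no contradiction; the bias is conditional on an effect on the control malformations.

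It can also be said that extraction fields and forest-plot splits belong in the SAP, that Newcastle-Ottawa appraisal covers control selection, and that 9.7 promises to discuss departures from the common-effect assumption. The SAP and Appendix 1 may hold more. But this protocol itself fixes eligibility, the outcome, the pooling model and the subgroup list, and neither an appraisal nor a discussion separates the two quantities.

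Finally, the odds ratio against non-malformed births is not plainly the better one, since it is more open to the recall bias that 9.9 names. That stands, and it is why the fix does not make either estimate primary.

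**Conclusion.** The point holds as a gap in the plan. Sections 9.2.1 and 9.7 together allow two different quantities, OR(cleft) and OR(cleft)/OR(other malformations), to be pooled as one, and no planned analysis would separate them. The harm is conditional on two things the protocol does not establish: that some of the 18 studies use malformed controls, and that exposure raises those control malformations. If both hold, the pooled OR is too low. On an assumed true OR of 1.5 the illustrated range runs from 1.43 (OR(other) 1.2, 25% of the weight) to 1.11 (OR(other) 1.5, 75% of the weight). If either fails, this bias is zero. Its actual size cannot be determined from the protocol.

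**What to change.** 1. Add one field to the extraction table described in section 9.6: the study's outcome reference group, coded as all or non-malformed births, or as infants with other malformations.
2. Add to section 9.7 a prespecified subgroup or sensitivity analysis that reports the pooled OR separately by reference group, beside the overall OR, whatever the level of heterogeneity.
3. State how a difference will be read. Malformed controls that are themselves affected by exposure lower one estimate; recall bias raises the other. Both widen the gap in the same direction, so the gap alone does not say which is at work. Neither stratum needs to become primary.
4. If no study uses malformed controls, say so in one sentence; that closes the point.

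The cost is one extraction field and one more forest plot, with no new data. Intervals are wider within each stratum, and not always slightly: the SE factors of 1.15 to 2.0 shown above apply to the non-malformed stratum. The overall estimate keeps its precision because it is still reported.

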9.2.2 Representativeness

The recall of the performed SLR is considered as representative for the population of pregnant women using corticosteroids in early pregnancy or first trimester. The conclusions out of this research are expected to be as close as possible to a representative sample of these women.

Cleft palate, even being one of the most common congenital malformations, is too rare to conduct studies with an optimal representative sample. Furthermore, the ethical aspects of conducting interventional clinical trials in pregnant women to investigate the occurrence of congenital malformations in the offspring following drug exposure limit the availability of research in the area. Therefore it is justified to conduct this study in order to answer the research question.

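### Two exclusion criteria in section 9.2.1 are faulty: the outcome line repeats the inclusion line, and safety studies are excluded by focus rather than for lack of cleft data

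*Protocol*

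**What the plan says.** Section 9.2.1 introduces its two lists as the criteria actually used: "The selection criteria utilized in the SLR were the following". Three entries matter.

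- The inclusion list has "Outcomes: Incidence/ risk of cleft lip/palate in infants". The exclusion list has the same line in the same words.
- The exclusion list ends with a group defined by what a study focuses on. One entry is "Safety profiles of glucocorticoid or corticosteroid".
- Another entry in that group is "Adverse events for other drugs".

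The same section gives the aim as finding every study, observational or clinical trial, published up to 25 June 2018, and then reports: "Only 18 studies were shortlisted based on the inclusion criteria". Section 7 describes the French authority's request as a meta-analysis "encompassing all studies investigating a possible increase in the risk of cleft palates in neonates". Section 9.2.2 adds: "The recall of the performed SLR is considered as representative for the population of pregnant women using corticosteroids". For the detailed review methods the protocol refers to Appendix 1, whose content is not shown.

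**The concern.** Eligibility for this meta-analysis should depend on whether a study holds usable data on glucocorticoid exposure and clefts. The two focus-based entries depend instead on what a paper is mainly about. Section 7 classifies the project as a post-authorisation safety study, so a paper on the safety of corticosteroids in pregnancy is close to the centre of the question. If such a paper reports clefts as one of several malformations, the stated rule allows it to be discarded. A study of several drugs that includes glucocorticoids might be lost in the same way under the other-drugs entry, although that is less clear from the wording.

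The duplicated outcome line adds a second problem. The place where one expects a rule excluding studies without cleft data is taken by a line that contradicts the inclusion list. The selection of the 18 studies therefore cannot be reproduced from the protocol.

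At stake are the completeness of the evidence given to the authority and the basis for calling it representative.

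**Working it through.** There is no sample size, power or error rate to reproduce. The check is a comparison of the stated rules.

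**1. The outcome line**

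- Inclusion requires incidence or risk of cleft lip or palate in infants.
- Exclusion removes studies with the identical description.
- Applied literally, every study that passes the first fails the second, so 0 studies are eligible.
- Sections 9.1, 9.2, 9.2.1 and 9.5 all report 18 selected studies.
- Since 18 is not 0, the line was not applied as written. The likeliest explanation is a lost qualifier, such as a missing *no* or *other than*.

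**2. The safety-profile line**

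Take a registry cohort of women using corticosteroids in pregnancy that reports several malformations, clefts among them.

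- Population, pregnant women: met.
- Intervention, any glucocorticoid by any route: met.
- Comparator, any or none: met.
- Outcome, cleft incidence or risk: met.
- Design, observational, including registry data: met.
- Time and geography, no restriction: met.
- Exclusion for a focus on the safety profile of the class: can apply, and no shown text limits it to studies without cleft data.

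Unlike the outcome line, this rule can be followed exactly as written, and the report of 18 studies does not show that it was not.

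**3. Set against the protocol's claims**

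A rule that can remove a study meeting every inclusion criterion is not consistent with an aim of finding all studies (section 9.2.1), and it weakens the support for the representativeness statement (section 9.2.2).

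**4. Whether the planned analysis would repair a loss**

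- The funnel plot, Egger's test and Galbraith plot in section 9.7 use retained studies only.
- The sensitivity analysis in section 9.7 compares results with and without outliers among those same studies, and only if heterogeneity is high.
- None of these can restore an excluded study.
- The checklist in Annex 2, item 7.2, answers No on whether selection bias is addressed.

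**5. Size**

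Section 9.7 specifies fixed-effect inverse-variance weighting, and section 9.2 gives study sizes from 106 to 832,636. An omitted study could thus carry anything from negligible to substantial weight. The number excluded under these entries and their results are not given, so no shift in the pooled odds ratio can be calculated.

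**The case against.** The strongest reply is that the safety-profile entry should be read in its setting. It stands beside entries on cleft surgery, stress-related internal corticosteroids and genetic mutations, which are plainly off topic. Read that way, it removes general drug-safety papers and was never meant to override the inclusion criteria. Section 9.4 also describes real safeguards: two independent screeners at each level with a third to settle differences, unclear citations kept at title and abstract stage, and back references checked. The authority's request can be read as covering studies that set out to investigate clefts, not every safety paper with a cleft row in a table. Appendix 1 may define the exclusion more narrowly.

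Much of this stands. The benign reading is possible, and the safeguards lower the chance of a silent loss. They do not remove it: a paper that two screeners clearly judge to focus on safety is not unclear, and the written rule tells them to exclude it. Nor does a narrow reading of the request settle the matter, because section 9.2.1 states its own aim of finding all studies.

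Two stronger conclusions are tempting, and the document supports neither.

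- A reader might infer that cleft studies were excluded wholesale under the duplicated outcome line. The 18 shortlisted studies rule that out.
- A reader might infer that the lost studies were mostly null, so that the pooled odds ratio is biased upwards. No text supports this. Section 8 says the retained studies range from high to non-significant risk, so unremarkable results were not all filtered out. Any figure for such a bias would rest on assumed odds ratios and assumed information shares, and its direction would follow from the value chosen for the excluded studies.

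**Conclusion.** The point holds as a defect in the stated eligibility rules. The outcome exclusion is a contradiction in wording, with no sign that it affected selection. The safety-profile exclusion is the substantive part: it selects on focus, has no exception for studies with cleft data, and can remove studies that the protocol's own inclusion criteria admit. The other-drugs entry carries a similar but weaker risk.

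The loss of any particular study is not shown, and neither the number lost nor the direction of any bias can be derived from the document. The conclusion assumes that the criteria in section 9.2.1 are those used, as that section says. If Appendix 1 words them differently, or shows that no eligible record was lost, what remains is a wording correction and a reported count. The change should still be made, because the protocol states a specific rule that should not be followed as written, and nothing in the planned analysis can make up for a study it removes.

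**What to change.** 1. Correct the outcome exclusion to *no data on orofacial cleft*.
2. Restrict the safety-profile and other-drugs exclusions to studies with no extractable data on glucocorticoid exposure and clefts.
3. Re-screen only the records already retrieved that were excluded for one of these two focus reasons, and add any study that proves eligible.
4. Report the number excluded and reinstated, by reason, within the PRISMA reporting already planned in section 9.8.
5. Bring Appendix 1 and section 9.2.1 into line if their wording differs.

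No new search is needed. The cost is a modest re-screening, plus data extraction and Newcastle-Ottawa appraisal for each study added. The count of 18, and the review report dated 9 July 2018, may need updating.
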